## PROTOCOL SYNOPSIS

Title	A Prospective, Single-arm, Multicenter Study of the SAPIEN 3 Ultra System in Intermediate Risk Patients with Severe, Calcific, Aortic Stenosis Requiring Aortic Valve Replacement
Objective	To confirm the procedural safety and performance of the SAPIEN 3 Ultra System in subjects with severe, calcific aortic stenosis who are at intermediate operative risk for standard aortic valve replacement (AVR)
Study Device	SAPIEN 3 Ultra Delivery System with the SAPIEN 3 Ultra THV (20, 23 and 26 mm) and SAPIEN 3 THV (29 mm)
Study Design	Prospective, single-arm, multicenter study
Study Population	Subjects with symptomatic, severe, calcific, aortic stenosis requiring AVR who are at intermediate operative risk and have appropriate iliofemoral anatomy for transfemoral access.
Sample Size	Up to 110 subjects who have the procedure started
Study Sites	Up to 8 actively enrolling sites
Assessment Schedule	Screening, procedure, post-procedure, discharge, 30 days, 6 months and annually through 5 years
Primary Endpoint	The primary endpoint is procedural success defined as freedom from all of the following at exit from the procedure room: 

• Mortality

• Conversion to surgery

• Moderate or severe paravalvular regurgitation

Secondary Endpoints	The following secondary endpoints will be evaluated: 

• Major vascular complications through discharge

• Valve migration or embolization through discharge

Inclusion Criteria	Candidates must meet all of the following criteria to be included in the study: 

1. Severe, calcific aortic stenosis meeting the following transthoracic echocardiogram (TTE) criteria:

• Aortic valve area (AVA) <math>\leq 1.0 \text{ cm}^2</math> OR AVA index <math>\leq 0.6 \text{ cm}^2/\text{m}^2</math>

• Jet velocity <math>\geq 4.0 \text{ m/s}</math> OR mean gradient <math>\geq 40 \text{ mmHg}</math>

2. New York Heart Association (NYHA) functional class <math>\geq \text{II}</math>

3. Judged by the Heart Team to be at intermediate risk for open surgical therapy (i.e., predicted risk of surgical mortality <math>\geq 3\%</math> and <math>< 8\%</math> at 30 days, based on the Society of Thoracic Surgeons (STS) risk score and other clinical co-morbidities unmeasured by the risk calculator)

4. The subject has been informed of the nature of the study, agrees to its provisions and has provided written informed consent as approved by the Institutional Review Board/Ethics Committee of the respective

clinical site.

Exclusion Criteria	
Candidates will be excluded from the study if any of the following conditions are present:
 

1. Native aortic annulus size unsuitable for available THV sizes on 3D imaging analysis

2. Aortic valve is unicuspid, bicuspid or non-calcified

3. Pre-existing mechanical or bioprosthetic valve in any position. (Of note, mitral ring is not an exclusion)

4. Severe aortic regurgitation (> 3+)

5. Severe mitral regurgitation (> 3+) or <math>\geq</math> moderate stenosis

6. Ventricular dysfunction with left ventricular ejection fraction (LVEF) < 30%

7. Cardiac imaging (echocardiography, computed tomography and/or magnetic resonance imaging) evidence of intracardiac mass, thrombus or vegetation

8. Evidence of an acute myocardial infarction <math>\leq</math> 30 days before the valve implant procedure

9. Subjects with planned concomitant ablation for atrial fibrillation

10. Hypertrophic cardiomyopathy with obstruction (HOCM)

11. Coronary anatomy that increases the risk of coronary artery obstruction post-TAVR

12. Complex coronary artery disease (CAD):

a. Unprotected left main coronary artery

b. SYNTAX score <math>> 32</math> (in the absence of prior revascularization)

c. Heart Team assessment that optimal revascularization cannot be performed

13. Iliofemoral vessel characteristics that would preclude safe placement of the introducer sheath

14. Significant abdominal or thoracic aortic disease that would preclude safe passage of the delivery system

15. Active bacterial endocarditis within 180 days of the valve implant procedure

16. Stroke or transient ischemic attack within 90 days of the valve implant procedure

17. Symptomatic carotid or vertebral artery disease or successful treatment of carotid stenosis within 30 days of the valve implant procedure

18. Severe lung disease (Forced Ejection Volume 1 (FEV1) < 50% predicted) or currently on home oxygen

19. Severe pulmonary hypertension (e.g., pulmonary artery systolic pressure <math>\geq</math> 2/3 systemic pressure)

---------------------------	--

20. Hemodynamic or respiratory instability requiring inotropic support, mechanical ventilation or mechanical heart assistance within 30 days of the valve implant procedure
21. History of cirrhosis or any active liver disease
22. Renal insufficiency (estimated glomerular filtration rate (eGFR) < 30 mL/min per the Cockcroft-Gault formula) and/or renal replacement therapy at the time of screening
23. Leukopenia (WBC < 3000 cell/mL), anemia (Hgb < 9 g/dL), thrombocytopenia (Plt < 50,000 cell/mL), history of bleeding diathesis or coagulopathy or hypercoagulable states
24. Inability to tolerate or condition precluding treatment with antithrombotic therapy during or after the valve implant procedure
25. Absolute contraindications or allergy to iodinated contrast that cannot be adequately treated with pre-medication
26. Significant frailty as determined by the Heart Team (after objective assessment of frailty parameters)
27. Subject refuses blood products
28. Body mass index > 50 kg/m^2
29. Estimated life expectancy < 24 months
30. Positive urine or serum pregnancy test in female subjects of childbearing potential
31. Currently participating in an investigational drug or another device study. Note: Trials requiring extended follow-up for products that were investigational, but have since become commercially available, are not considered investigational trials. Observational studies are not considered exclusionary.

**Statistical Methods**

The success criterion for this study is procedural success of at least 90%. The primary statistical analysis for this study is to estimate the procedure success rate. With sample size of at least 55 subjects, if the observed rate is at least 90%, the lower bound of the observed 95% CI (calculated from binomial distribution) will be at least 80%. Descriptive summary statistics will be provided.

## 1 INTRODUCTION

### 1.1 Aortic Stenosis

Aortic stenosis (AS) is one of the most common valvular diseases in developed countries, affecting ~5% of adults above the age of 65, and its prevalence is projected to increase over the next decade with an aging population (1, 2). AS is a progressive, debilitating and life-threatening disease if left untreated. The pathology involves progressive calcification of the leaflets that results in stenosis which limits valve opening. The consequences of valve obstruction include increased afterload, left ventricular hypertrophy, and a decrease in systemic and coronary blood flow. Typically, patients with AS are free from cardiovascular symptoms (e.g. angina, syncope, and/or heart failure) until late in the course of the disease. However, once symptoms manifest, the prognosis is poor without intervention. Survival analyses have demonstrated that the interval from onset of symptoms to time of death is approximately two years in patients with heart failure, three years in those with syncope, and five years in those with angina (3).

### 1.2 Treatment of AS

Relief of aortic valve obstruction typically results in an improvement of symptoms, hemodynamic parameters, and global left ventricle systolic function, as well as reversal of left ventricular hypertrophy (4, 5). Treatment options for patients with severe, symptomatic AS include medical management, percutaneous balloon aortic valvuloplasty (BAV) or aortic valve replacement (AVR).

AVR is considered the gold standard for treatment of patients with severe, symptomatic AS (6). AVR may be performed surgically or percutaneously. Outcomes after surgical AVR (SAVR) are excellent in patients who do not have a high procedural risk, resulting in an improvement in symptoms, and in most patients, an improvement in exercise tolerance (7-11).

Transcatheter aortic valve replacement (TAVR) was originally developed as an alternative to SAVR in patients who were at high risk for surgical mortality or who were not suitable for surgical intervention, with the first successful TAVR procedure performed by Cribier and colleagues in 2002 (12).

The Placement of AoRtic TranNscathetER valve (PARTNER) study, Cohort B compared standard medical therapy (including BAV) to TAVR in patients with severe AS who were not candidates for surgical intervention. Mortality rates at 1 year were significantly lower in the TAVR cohort compared to those who underwent medical therapy (30.7% vs. 50.7%, p<0.001) (13). At 5-years, 71.8% of TAVR patients had died compared to 93.6% of patients treated medically (p<0.0001) (14).

Numerous studies have since been performed comparing TAVR to SAVR. Studies comparing the two treatments in patients at high surgical risk have demonstrated the superiority of outcomes with TAVR compared to SAVR (15-17)

In the PARTNER II study evaluating outcomes of TAVR with SAPIEN XT vs SAVR in intermediate risk patients, there was no difference between TAVR and SAVR for the primary endpoint of all-

cause death or disabling stroke at 2 years (Hazard Ratio: 0.89; 95% Confidence Interval (CI): 0.73 to 1.09;  $p=0.25$ ). All-cause mortality occurred in 16.7% of those randomized to TAVR with SAPIEN XT, compared with 18.0% of those treated with SAVR. Disabling stroke occurred in 6.2% of patients treated with TAVR and 6.3% of patients treated with SAVR (18). In a propensity score-matched comparison of the SAPIEN 3 TAVR patients and PARTNER II Cohort A SAVR patients, TAVR demonstrator noninferiority and superiority to SAVR (propensity score pooled weighted proportion difference: -9.2%; 95% CI: -13.0 to -5.4;  $p<0.0001$ ). At 1 year, the rate of all-cause death was 7.4%, disabling stroke occurred in 2%, reintervention was required in 1%, and moderate or severe paravalvular leak (PVL) was seen in 2% (19).

As a result of these and other findings, the American College of Cardiology (ACC)/American Heart Association (AHA) guideline committees have provided TAVR with a Class I and IIa recommendation for patients with severe AS with high/prohibitive and intermediate surgical risk, respectively (20). And according to the 2017 European Society of Cardiology (ESC)/ European Association for Cardio-Thoracic Surgery (EACTS) guidelines on valvular heart diseases, TAVR is favored over SAVR in elderly patients with suitable transfemoral access and elevated surgical risk (21).

This study will evaluate the SAPIEN 3 Ultra System. The SAPIEN 3 Ultra THV design differs from the SAPIEN 3 design only with respect to the weave of the outer skirt and attachment of the skirt to the frame. The SAPIEN 3 Ultra Delivery System allows the THV to be crimped directly onto the deployment balloon eliminating the need for valve alignment and reducing the number of procedural steps.

## 2 STUDY OBJECTIVE

The objective of this study is to confirm the procedural safety and performance of the SAPIEN 3 Ultra System in subjects with severe, calcific AS who are at intermediate operative risk for standard AVR.

### 2.1 Intended Use

The Edwards SAPIEN 3 Ultra valve and the Edwards SAPIEN 3 with the Edwards SAPIEN 3 Ultra delivery system and accessories are indicated for use in patients with severe, symptomatic, calcific aortic valve stenosis who are judged by a Heart Team, to be at intermediate or greater risk for open surgical therapy (i.e., predicted risk of surgical mortality  $\geq 3\%$  at 30 days, based on the Society of Thoracic Surgeons (STS) risk score and other clinical comorbidities unmeasured by the STS risk calculator).

## 3 STUDY DESIGN

This is a prospective, single-arm, multicenter study. Up to 110 subjects will undergo the procedure at up to 8 participating centers. Subject follow-up will occur at 30 days, 6 months and annually through five years.

## 4 STUDY DEVICES

The following devices and accessories will be used per the Instructions for Use (IFU) and after sufficient training has been provided by Edwards.

### 4.1 Edwards SAPIEN 3 Ultra THV

The Edwards SAPIEN 3 Ultra THV is comprised of a balloon-expandable, radiopaque, cobalt-chromium frame, trileaflet bovine pericardial tissue valve, and polyethylene terephthalate (PET) inner and outer fabric skirts. The leaflets are treated according to the Carpentier-Edwards ThermaFix process. See **Table 1** for THV sizing recommendations.

### 4.2 Edwards SAPIEN 3 THV

The Edwards SAPIEN 3 THV is comprised of a balloon-expandable, radiopaque, cobalt-chromium frame, trileaflet bovine pericardial tissue valve, and PET inner and outer fabric skirts. The leaflets are treated according to the Carpentier-Edwards ThermaFix process. See **Table 1** for THV sizing recommendations.

The THV is intended to be implanted in a native annulus size range associated with the three-dimensional area of the aortic annulus measured at the basal ring during systole.

**Table 1: THV Sizing Dimensions**

Native Valve Annulus Size (TEE)*	Native Valve Annulus Size (CT)		THV Size
	Area	Area Derived Diameter	
16 – 19 mm	273 – 345 mm 	18.6 – 21.0 mm	20 mm
18 – 22 mm	338 – 430 mm 	20.7 – 23.4 mm	23 mm
21 – 25 mm	430 – 546 mm 	23.4 – 26.4 mm	26 mm
24 – 28 mm	540 – 683 mm 	26.2 – 29.5 mm	29 mm

\*Due to limitations in two-dimensional images, 2-D TEE imaging should be supplemented with 3-D area measurements.

THV size recommendations are based on native valve annulus size, as measured by transesophageal echocardiography (TEE) or computed tomography (CT). Patient anatomical factors and multiple imaging modalities should be considered during THV size selection. Note: Risks associated with undersizing and oversizing should be considered to minimize the risk of paravalvular leak, migration and/or annular rupture.

### 4.3 Edwards SAPIEN 3 Ultra Delivery System

The Edwards SAPIEN 3 Ultra delivery system which is used for delivery of the Edwards SAPIEN 3 Ultra THV and the Edwards SAPIEN 3 THV consists of a Flex Catheter to aid in tracking, and THV positioning. The delivery system includes a tapered tip to facilitate crossing of the native valve. The handle contains a Flex Wheel to control flexing of the Flex Catheter, and the Fine Adjustment Wheel to facilitate THV positioning within the native annulus. A stylet is included within the guidewire lumen of the delivery system. A radiopaque Positioning Marker in the balloon is provided to assist with THV positioning.

The Qualcrimp crimping accessory (packaged with the Edwards SAPIEN 3 Ultra delivery system) is used during THV crimping.

The loader (packaged with the Edwards SAPIEN 3 Ultra delivery system) is used to aid insertion of the delivery system into the sheath.

#### **4.4 Edwards Axela Sheath**

The Edwards Axela sheath is intended for introduction and removal of devices used with the Edwards SAPIEN 3 Ultra THV System.

The Edwards Axela Sheath contains:

- a) An expandable sheath with hydrophilic coating that provides access into the target vessel while maintaining hemostasis and temporarily enlarges its diameter to allow for passage of a device.
- b) Two dilators with hydrophilic coating that can either be used to dilate the vessel to accommodate the Edwards Axela sheath and/or facilitate entry and trackability of the sheath into the vessel.

#### **4.5 Edwards eSheath Introducer Set**

The Edwards eSheath Introducer Set contains:

- a) An expandable sheath (eSheath) that provides access into the target vessel while maintaining hemostasis and temporarily enlarges its diameter to allow for passage of a device.
- b) Two dilators with hydrophilic coating that can either be used to dilate the vessel to accommodate the eSheath and/or facilitate entry and trackability of the eSheath into the vessel.

The eSheath has been approved for use and is commercially available with the SAPIEN 3 THV.

#### **4.6 Edwards Crimper and Crimp Stopper**

The Edwards crimper reduces the diameter of the valve to mount it onto the delivery system. The crimper is comprised of a housing and a compression mechanism that is closed with a handle located on the housing. A 2-piece crimp stopper (packaged with the delivery system) is used to crimp the valve to its intended diameter.

#### **4.7 Edwards Transfemoral Balloon Catheter, 25 mm**

The Edwards Transfemoral Balloon Catheter, 25 mm size, consists of a shaft and balloon with two radiopaque marker bands that indicate the working length of the balloon. The proximal end of the device has a “Y-connector” with a balloon inflation port labeled as “BALLOON” and a guidewire lumen port labeled as “WIRE”.

## 5 STUDY ENDPOINTS

### 5.1 Primary Endpoint

The primary endpoint is procedural success defined as freedom from all of the following at exit from the procedure room:

- Mortality
- Conversion to surgery
- Moderate or severe paravalvular regurgitation

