### **7.3 Procedure**

The study devices will be used per the most current IFU for device sizing, preparation and recommended implant procedure. Only physicians appropriately trained to the use of the device and identified on the Delegation of Authority (DoA) log on file with Edwards may perform the implant procedure in study subjects.

The valve implant procedure will be considered to have started when the first interventional access-related puncture (arterial) is established. It is strongly encouraged that the procedure be performed within 14 days of Case Review Board approval.

Procedure assessments will include the following:

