## 7.9 Subject Disposition

The following categories of subject disposition have been defined for this trial:

**Enrolled**: Subjects will be considered enrolled once the ICF is signed and dated.

**Discontinued**: Enrolled subjects will be considered discontinued when they exit the study prior to completing all required follow-up. Potential reasons include but are not limited to:

- **Study Procedure Never Started**: Subjects considered enrolled that do not meet pre-procedure eligibility criteria will be exited from the study.
- **Procedure Started but Study Device Never Implanted**: Subjects in whom the procedure was started but did not receive a study valve will be followed for 30 days or until resolution of any adverse events related to the valve implant procedure and then exited from the study.
- **Study Device Explanted**: Subjects who have a surgical reintervention where the study valve is explanted will be followed for 30 days post-reintervention or until resolution of any adverse events related to the procedure and then exited from the study.

Subjects that have a valvuloplasty or valve-in-valve procedure will continue to be followed for the duration of the study.

If a subject discontinues, all attempts should be made to have the subject come into the clinic for an exit visit. An exit form indicating the reason for discontinuation will be completed. Subjects who discontinue will not be replaced.

**Completed**: Enrolled subjects will be considered to have completed the study when all required follow-up has been performed.

**Table 3** summarizes the subject assessments at each time point.

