## 10 STATISTICAL ANALYSIS

### 10.1 Analysis Populations

Enrolled subjects will consist of all subjects who sign and date the ICF.

- The As Treated (AT) population is defined to include all enrolled subjects for whom the valve implant procedure was started.
- The Valve Implant (VI) population is the subset of the AT population consisting of all subjects who receive and retain the study valve upon leaving the procedure room. If it is necessary to implant more than one study valve (valve-in-valve), the subject will still be in the VI population..

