I	Patients with cardiac disease but without resulting limitation of physical activity. Ordinary physical activity does not cause undue fatigue, palpitation, dyspnea or anginal pain.											
II	Patients with cardiac disease resulting in slight limitation of physical activity. They are comfortable at rest. Ordinary physical activity results in fatigue, palpitation, dyspnea or anginal pain.											
III	Patients with cardiac disease resulting in marked limitation of physical activity. They are comfortable at rest. Less than ordinary activity causes fatigue, palpitation, dyspnea or anginal pain.											
IV	Patients with cardiac disease resulting in inability to carry on any physical activity without discomfort. Symptoms of heart failure or the anginal syndrome may be present even at rest. If any physical activity is undertaken, discomfort is increased.											
Paravalvular Leak (PVL)	
Paravalvular or paraprosthetic leak is a complication associated with the implantation of a prosthetic heart valve whether traditional (surgical) or a transcatheter (TAVR) approach.
 
PVL refers to blood flowing through a channel between the structure of the implanted valve and cardiac tissue as a result of a lack of appropriate sealing
	ESC										
Peripheral Vascular Disease (PWD)	
Includes peripheral arterial disease of upper and lower extremity, renal, mesenteric, and abdominal aortic systems, as follows:
 
 
• Claudication, either with exertion or at rest
 
• Amputation for arterial vascular insufficiency
 
• Vascular reconstruction, bypass surgery, or percutaneous intervention to the extremities (excluding dialysis fistulas and vein stripping)
 
• Documented abdominal aortic aneurysm with or without repair
 
• Positive noninvasive test (e.g., ankle brachial index < 0.9, ultrasound, magnetic resonance or computed tomography imaging of > 50% diameter stenosis in any peripheral artery, i.e., renal, subclavian, femoral, iliac) or angiographic imaging
 
 
Peripheral arterial disease excludes disease in the carotid, cerebrovascular arteries or thoracic aorta.
 
PVD does not include DVT.
	STS										

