STS Adult Cardiac Surgery Risk Calculator	The Society of Thoracic Surgeons' risk models predict the risk of operative mortality and morbidity after adult cardiac surgery on the basis of subject demographic and clinical variables. http://riskcalc.sts.org/stswebriskcalc/#/	STS
Syncope	A fainting spell or loss of consciousness	STS
SYNTAX Score	An angiographic grading tool to determine the complexity of CAD. http://www.syntaxscore.com/ http://ir-nwr.ru/calculators/syntaxscore/frameset.htm	

Term	Definition	Reference/ Justification
THV-in-THV	An additional valve prosthesis is implanted within a previously implanted prosthesis because of suboptimal device position and/or function, during or after the valve implant procedure	VARC-2
Transient Ischemic Attack (TIA)	See "Stroke / Transient Ischemic Attack (TIA)"	
Valve Implant Procedure	
Placement of study device and/or additional procedures occurring in the procedure room which are completed prior to subject transfer to a post-procedure recovery unit (e.g. Recovery Room, ICU/CCU, etc.).
 
The valve implant procedure will be considered to have started when the first interventional access-related puncture (arterial) is established. The end of valve implant procedure is defined as date and time of vascular closure post-eSheath removal.
 
Performance of TEE does not by itself constitute start of procedure
	Sponsor
Valve Malpositioning	
Valve migration
 
 
After initial correct positioning, the valve prosthesis moves upward or downward, within the aortic annulus from its initial position, with or without consequences
 
 
Valve embolization
 
 
The valve prosthesis moves during or after deployment such that it loses contact with the aortic annulus
 
 
Ectopic valve deployment
 
 
Permanent deployment of the valve prosthesis in a location other than the aortic root
 
	VARC-2

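### Procedural success in 5.1 does not require that a valve be implanted, so a started procedure that ends with no valve, in a living and unconverted subject, reads as a success in AT and drops out of VI, and 10.1 names neither population as primary

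*Combined protocol and SAP*

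**What the plan says.** **Endpoint.** Section 5.1 reads "The primary endpoint is procedural success defined as freedom from all of the following at exit from the procedure room". The listed events are death, conversion to surgery, and moderate or severe paravalvular regurgitation. The synopsis gives the same definition. Appendix B has no entry for procedural success or for conversion to surgery.

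**Regurgitation.** The Appendix B entry on paravalvular leak says "PVL refers to blood flowing through a channel between the structure of the implanted valve and cardiac tissue".

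**Start of procedure.** Section 7.3: "The valve implant procedure will be considered to have started when the first interventional access-related puncture (arterial) is established". Appendix B adds: "Performance of TEE does not by itself constitute start of procedure".

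**Populations.** Section 10.1: "The As Treated (AT) population is defined to include all enrolled subjects for whom the valve implant procedure was started". VI is the subset of AT "consisting of all subjects who receive and retain the study valve upon leaving the procedure room", and a subject with a second study valve placed inside the first stays in it. Sections 10.1 to 10.3 and the synopsis do not assign the primary endpoint to either population. The sample size in the synopsis is counted as "Up to 110 subjects who have the procedure started".

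**Non-implants.** Section 7.9 foresees them: "Subjects in whom the procedure was started but did not receive a study valve will be followed for 30 days", or until related adverse events resolve. Section 7.3 also lets an aborted procedure be re-scheduled, before or after its start, and does not say which attempt is scored.

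**Criterion.** Section 10.2 requires observed success of at least 90%. It adds that with at least 55 subjects the lower 95% binomial limit will then be at least 80%.

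**The concern.** Section 2 sets out to confirm procedural safety and performance of the system, and Section 1.2 presents a delivery system that works differently from its predecessor. Failure to place a valve is a performance result. The only valve-related component of the endpoint is paravalvular regurgitation, which presupposes a valve. When no valve is placed that component cannot fail, and the subject is left with death and conversion as the only ways to be a failure.

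Neither population repairs this. AT keeps the subject and, read literally, counts a success. VI removes the subject from numerator and denominator. If an analyst calls regurgitation not evaluable, no written rule covers the case, and it is still not a failure. What is at stake is the primary rate, its confidence interval and the 90% criterion.

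**Working it through.** **1. The plan's own figure.** 0.90 × 55 = 49.5, so the smallest count that meets 90% is 50. The exact (Clopper-Pearson) lower limit is the 0.025 quantile of Beta(x, n − x + 1). For x = 50 and n = 55 it is 80.05%, so the stated 80% is reproduced at n = 55. (It does not hold at 60, where 54/60 gives 79.5%, or at 61, where 55/61 gives 79.8%. That is a separate matter and plays no part here.)

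**2. What the rule tolerates.** Let f be the subjects with a listed event and k the living, unconverted subjects who leave with no valve and have no later attempt.

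- As written in AT, success = (n − f)/n. The criterion is met if f ≤ 5 at n = 55, or f ≤ 11 at n = 110, whatever k is.
- With no-valve exits counted, success = (n − f − k)/n. The criterion is met if f + k ≤ 5, or f + k ≤ 11.

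| n | f | k | AT as written | k counted as failures |
|---|---|---|---|---|
| 55 | 5 | 1 | 50/55 = 90.9% (lower limit 80.05%) | 49/55 = 89.1% (77.8%) |
| 110 | 11 | 1 | 99/110 = 90.0% (82.8%) | 98/110 = 89.1% (81.7%) |
| 110 | 8 | 3 | 102/110 = 92.7% (86.2%) | 99/110 = 90.0% (82.8%) |
| 110 | 8 | 4 | 102/110 = 92.7% (86.2%) | 98/110 = 89.1% (81.7%) |

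**3. The unnamed population.** With n = 110, f = 11 and k = 1, AT as written is 99/110 = 90.0% (met). If all 11 failures kept their valve, VI is 98/109 = 89.9% (not met). The choice of population can therefore decide the result by itself.

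**4. Chance of meeting 90%.** Let o be the rate of listed failures and r the rate of no-valve exits. Both are assumed, because the documents give neither. Subjects are taken as independent, the two kinds of outcome as mutually exclusive, and no repeat attempts are made.

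- As written (AT): P(X ≥ 50), X ~ Binomial(55, 1 − o); or P(X ≥ 99), X ~ Binomial(110, 1 − o).
- Counted: the same with success probability 1 − o − r.

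| o | r | n = 55, as written | n = 55, counted | n = 110, as written | n = 110, counted |
|---|---|---|---|---|---|
| 2% | 1% | 0.999 | 0.994 | 1.000 | 1.000 |
| 3% | 1% | 0.994 | 0.978 | 1.000 | 0.998 |
| 5% | 1% | 0.944 | 0.889 | 0.991 | 0.967 |
| 5% | 3% | 0.944 | 0.724 | 0.991 | 0.831 |
| 8% | 3% | 0.724 | 0.428 | 0.831 | 0.443 |

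**5. Why VI is not in the table.** Its probability depends on how many of the other failures also lack a retained valve, which conversions to surgery may well do. At n = 110, o = 8% and r = 3%, the VI probability is 0.739 if every other failure keeps the valve and 0.994 if half do not. The AT value of 0.831 lies between the two, so even the direction of the VI–AT difference is unsettled.

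**The case against.** **Such exits may be rare.** The protocol's nearest figure is 2% moderate or severe leak at 1 year with the predecessor valve (Section 1.2), which is one component at a different time point. At 2% and 1% the effect is 0.005 with 55 subjects and nil to three decimals with 110. This stands: the effect is negligible at low rates.

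**The cases are visible elsewhere.** Disposition (7.9), device-deficiency reports (8.1) and the secondary endpoint on migration or embolization (5.2) would show some of them. This also stands, but none of these enters the primary rate, its interval or the criterion.

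**AT is implied.** The sample size counts started procedures, which is the AT denominator. That is a fair hint, but it does not assign the endpoint, and AT is where the literal reading gives a success.

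**Stronger readings to avoid.** A reader might infer that a procedure without a study valve can never be a failure. That is not so. Death and conversion count in AT, and Appendix B describes paravalvular leak for surgical and transcatheter prostheses alike, so a subject leaving with a non-study prosthesis and moderate or severe leak also fails. A reader might also infer that every no-valve exit is a device failure. Table 2 foresees an abort for thrombus found during the procedure, and if that happens after puncture it is a no-valve exit for another reason. An abort before puncture is not a started procedure at all.

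Finally, one might argue that VI breaks the 80% statement, since 49/54 = 90.7% has a lower limit of 79.7%. This arises only if enrolment stops near 55, the shortfall is 0.3 percentage points, and the success criterion is the observed 90%.

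**Conclusion.** The point holds in this form: on the literal text, a started procedure that ends with no prosthesis in a living, unconverted subject is a success in AT, or unscored if regurgitation is called not evaluable. It is excluded from VI, and the primary population is not named. For an objective that includes performance, this is a fault in the endpoint's construction and more than a missing detail.

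Its size rests on assumed rates. The loss in the chance of meeting 90% when such exits are counted runs from 0.005 (n = 55, 2% and 1%) to 0.220 (n = 55, 5% and 3%: 0.944 − 0.724). At n = 110 it runs from nil to three decimals to 0.160 (0.991 − 0.831) at the same rates. At 8% and 3% it is larger still, but nothing in the documents suggests that those rates are likely. Independently of any rate, one subject reverses the result when the count is at the threshold. For subjects later re-scheduled and implanted, nothing is overstated if the later attempt is scored. The documents do not support a claim that the reported rate will be materially wrong, only that the plan would not detect it if it were. It should be fixed before data review.

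**What to change.** 1. In 5.1 and the synopsis, add to procedural success that a study valve is implanted and retained at exit from the procedure room. Use the VI wording, so that a second study valve inside the first still qualifies.
2. In 10.1, name AT as the primary analysis population and VI as supportive.
3. Score a started procedure with no study valve and no later attempt as a failure.
4. For a procedure aborted after puncture and re-scheduled, state before data review which attempt is scored, and report the other as a sensitivity analysis. Scoring the last attempt hides a first delivery failure; scoring the first ignores a later success.
5. List the number of no-valve exits and the reason for each. Add a sensitivity analysis that sets aside aborts for non-device reasons, using the reason recorded at the time.
6. State that aborts before arterial puncture stay outside AT.

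**Cost.** Section 12.6 requires a written amendment, submission to the ethics committee and regulators as applicable, approval at each site, and any required training. Little new data is needed, since valve receipt and retention already define VI and 7.9 already classifies non-implants. The case report forms are not in the documents, so a field for the abort reason should be checked. The unchanged 90% criterion becomes slightly stricter and the reported rate may be a little lower, so the sponsor should confirm that 90% still applies.
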